8.7. Data analysis

Analyses will initially be conducted separately within the data from each data source. Data source–specific results will be returned to the study coordinating center, which will aggregate results across the data sources for reporting. Pooled analysis of RR and prevalence ratio estimates from all data sources will be conducted using privacy-preserving summary-level data sets (e.g., risk set–level data sets) or if this is not feasible, meta-analysis. Detailed methodology for summary and statistical analyses of data collected in this study will be documented in the SAP, which will be dated, filed, and maintained by the sponsor. The SAP may modify the plans outlined in the protocol; any major modifications of primary outcome definitions or their analyses will be reflected in a protocol amendment.

8.7.1. Descriptive analysis

Descriptive analysis will report on utilization of Pfizer-BioNTech original monovalent COVID-19 Vaccine during the overall study period and during the study period, stratified in 12-week increments (to assess vaccine uptake and patterns of exposure over time). The proportion of individuals receiving at least 1 dose, at least 2 doses, and at least 3 doses of Pfizer-BioNTech original monovalent COVID-19 Vaccine will be estimated within the overall study population, among individuals who are immunocompromised, among individuals with a history of COVID-19, and among pregnant women. If additional doses of Pfizer-BioNTech original monovalent COVID-19 Vaccine are authorized and available in the data sources, the proportion of individuals receiving additional doses (at least 4 doses, at least 5 doses, etc.) will also be described.

PFIZER CONFIDENTIAL CT24-WI-GL02-RF02 3.0 Non-Interventional Study Protocol Template For Secondary Data Collection Study 20-May-2021 Page 89 of 120 Among individuals who receive a second dose of Pfizer-BioNTech original monovalent COVID-19 Vaccine, the proportion of individuals will be reported by type of second dose of COVID-19 vaccine, and time between the first and second doses will be described within the overall study population, among pregnant women, among immunocompromised individuals, among individuals with a history of COVID-19, and stratified by age (6 months through 4 years and \geq 5 years). Among individuals who receive a third dose of Pfizer-BioNTech original monovalent COVID-19 Vaccine, the proportion of individuals will be reported by type of third dose of COVID-19 vaccine, and time between the second and third doses will be described within the overall study population, among pregnant women, among immunocompromised individuals, among individuals with a history of COVID-19 vaccine, and time between the second and third doses will be described within the overall study population, among pregnant women, among immunocompromised individuals, among individuals with a history of COVID-19, and stratified by age (6 months through 4 years and \geq 5 years).

Additionally, characteristics (i.e., demographics, comorbidities, and other potential covariates) of the matched and unmatched study cohorts will be shown in a table. No statistical tests are planned for this comparison, but the balance of variables in the matched cohorts will be assessed using standardized differences or other suitable methods.

The following descriptive analyses will be performed for specific safety events of interest:

- The number and proportion of individuals with a convulsion event who have a history of epilepsy will be reported separately in each of the matched exposed and matched unexposed cohorts.
- The length of FU in the exposed and unexposed cohorts contributing to analyses of vaccine-associated enhanced disease will be output.
- The proportion of myocarditis/pericarditis cases with subsequent serious cardiovascular conditions (up to 1 year after diagnosis, using all available data) will be estimated among individuals vaccinated with Pfizer-BioNTech original monovalent COVID-19 Vaccine and in individuals not vaccinated with a COVID-19 vaccine, using structured data from claims and electronic health records (where available, as not all research partners have electronic health records data available in the Sentinel Distributed Database). These analyses will be described in the SAP.

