- 3. In individuals aged 5 years and older who have received 2 doses in a primary series¹ of Pfizer-BioNTech original monovalent COVID-19 Vaccine: To estimate the RR of safety events of interest (including myocarditis/pericarditis) following a third dose (as an additional dose in a primary series¹ or as a booster dose) of Pfizer-BioNTech original monovalent COVID-19 Vaccine received more than 2 months after the second dose compared with that among individuals without a third dose of any COVID-19 vaccine

Among pregnant women:

4. To estimate the birth prevalence and prevalence ratio of birth outcomes among infants born to pregnant women vaccinated with Pfizer-BioNTech original monovalent COVID-19 Vaccine compared with that among infants born to unvaccinated pregnant women.

Secondary objectives:

Among the overall study population and subgroups of pregnant women, immunocompromised individuals, and individuals with a history of COVID-19:

- 1. To describe the proportion of individuals receiving Pfizer-BioNTech original monovalent COVID-19 Vaccine, stratified by number of doses
- 2. To describe—among individuals who have received a first dose of Pfizer-BioNTech original monovalent COVID-19 Vaccine—the timing and type of second dose of COVID-19 vaccine (Pfizer-BioNTech original monovalent COVID-19 Vaccine or other COVID-19 vaccine)

- 3. To describe baseline characteristics (demographics and comorbidities) of individuals who have received at least 1 dose of Pfizer-BioNTech original monovalent COVID-19 Vaccine and those with no record of COVID-19 vaccination of any type
- 4. To describe—among individuals who have received 2 doses of Pfizer-BioNTech original monovalent COVID-19 Vaccine—the timing and type of a third dose of COVID-19 vaccine (Pfizer-BioNTech original monovalent COVID-19 Vaccine or other COVID-19 vaccine)
- 5. To describe—among individuals aged 5 years and older who have received at least 2 doses in a primary series¹ of Pfizer-BioNTech original monovalent COVID-19 Vaccine—baseline characteristics (demographics and comorbidities) of individuals who received a third dose (either as an additional dose in a primary series¹ or as a booster dose) of Pfizer-BioNTech original monovalent COVID-19 Vaccine more than 2 months after the second dose and those with no record of a third dose of COVID-19 vaccination of any type

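### Section 8.7.1 describes the type of the second and third dose only in people for whom that dose was the study vaccine, contrary to secondary objectives 2 and 4

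*Protocol*

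**What the plan says.** Section 7 of the protocol sets two descriptive secondary objectives about the next dose. Objective 2 concerns "individuals who have received a first dose of Pfizer-BioNTech original monovalent COVID-19 Vaccine—the timing and type of second dose of COVID-19 vaccine". Objective 4 concerns "individuals who have received 2 doses of Pfizer-BioNTech original monovalent COVID-19 Vaccine—the timing and type of a third dose of COVID-19 vaccine". Both define type by the same two categories: "Pfizer-BioNTech original monovalent COVID-19 Vaccine or other COVID-19 vaccine". The title-page table and the abstract give the same populations.

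Section 8.7.1 is where these descriptions are specified. For the second dose it says: "Among individuals who receive a second dose of Pfizer-BioNTech original monovalent COVID-19 Vaccine, the proportion of individuals will be reported by type" of second dose, together with the time between the first and second doses. For the third dose it says: "Among individuals who receive a third dose of Pfizer-BioNTech original monovalent COVID-19 Vaccine, the proportion of individuals will be reported by type" of third dose, together with the time between the second and third doses. Both are to be given overall, in pregnant women, in immunocompromised individuals, in individuals with a history of COVID-19, and by two age groups.

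The same section plans one other utilization output: "The proportion of individuals receiving at least 1 dose, at least 2 doses, and at least 3 doses of Pfizer-BioNTech original monovalent COVID-19 Vaccine", overall and in the three subpopulations.

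**The concern.** The objectives start from people who have had the preceding study-vaccine dose or doses and ask what came next. Section 8.7.1 starts from people whose next dose is already known to be the study vaccine and then asks what type it was. The selection fixes the variable being tabulated.

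If the table is programmed as written, the brand part of both objectives is lost, and the timing part covers only those who came back for the same product. A reader of the report could take a 100% figure as a finding about brand adherence when it is a consequence of the selection.

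**Working it through.** The protocol states no figure for this analysis, so there is none to reproduce. The check compares the populations.

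**1. Populations side by side**

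| Description | Population in Section 7 | Population in Section 8.7.1 |
|---|---|---|
| Type and timing of second dose | Received a first study-vaccine dose (objective 2) | Received a second dose that was the study vaccine |
| Type and timing of third dose | Received 2 study-vaccine doses (objective 4) | Received a third dose that was the study vaccine |

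**2. What each defines.** Let D1, D2, D3 be the brand of the first, second and third recorded COVID-19 vaccine dose: S for the study vaccine, O for another brand, N for none recorded.

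- Objective 2 asks for P(D2 = S | D1 = S) and P(D2 = O | D1 = S). Objective 4 asks for the same with D3, given D1 = D2 = S. Both are free to take any value.
- Section 8.7.1 gives P(D2 = S | D2 = S) = 1 and P(D2 = O | D2 = S) = 0. The third dose gives the same 1 and 0. These hold in every subpopulation and age group.

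**3. Timing.** Section 8.7.1 gives the interval between doses when the later dose is S. The objectives also cover the interval when the later dose is O. Timing is therefore truncated, not absent.

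**4. Does another planned output fill the gap?** Write n1, n2, n3 for the numbers with at least 1, 2 and 3 study-vaccine doses. Then n2/n1 approximates P(D2 = S | D1 = S), and n3/n2 does the same for the third dose. The remainder, 1 − n2/n1, is P(O) + P(N), and these counts cannot divide it.

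An illustration with assumed figures, since the protocol gives none: of first-dose recipients, 85% take the same brand, 3% another brand, 12% none.

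- n2/n1 = 85%, so the same-brand share is recoverable. The other 15% (3% + 12%) is reported as one lump.
- Among those with any second dose, the share with the study vaccine is 85/(85 + 3) = 96.6%. The type table in 8.7.1 would show 100%.
- Holding n2/n1 at 85%, the other-brand share could lie anywhere from 0% to 15%. The share with the study vaccine among second doses would then lie between 100% (85/85) and 85% (85/100). The planned outputs would be identical across that whole range.

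The ratio is itself approximate. Someone with the sequence study, other, study counts in n2. Section 6 records authorization of the study vaccine as a booster after another brand, and such a person counts in n1.

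**5. A second reading of the wording.** If a second dose of the study vaccine means the second study-vaccine record, and not the second COVID-19 dose, the sequence study, other, study could yield a non-study type. People who switched and did not return would still be left out, so the objectives' population is not recovered.

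**6. Can the missing category occur, and can it be measured?** Section 6 describes a recommendation allowing a different brand as booster for adults who completed a study-vaccine primary series, so at least for the third dose the category is a real possibility. Section 8.3.1 plans to identify the other COVID-19 vaccines in the same way as the study vaccine, so the data will be held.

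**The case against.** The strongest reply is that this is a drafting slip. The objectives are stated correctly in three places, and the 8.7.1 sentences presuppose more than one type, so nobody meant to choose a different population. The version 2.0 entry in the amendment log also words the third-dose analysis with the two-dose population; that is context only and nothing here relies on it. Section 8.7 adds that "The SAP may modify the plans outlined in the protocol", and the SAP is not at hand.

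It probably is a slip. That does not remove the contradiction: 8.7.1 does not leave the population open but states one, and a programmer following it literally gets the degenerate table. Section 8.7 calls for a protocol amendment only for major changes to primary outcome definitions or their analyses, so a correction made only in the SAP would leave the protocol inconsistent.

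A reader might infer that objectives 2 and 4 cannot be answered at all. The protocol does not support that. Same-brand intervals are still described, and the at-least-1, -2 and -3 proportions give roughly the same-brand continuation share. Brand data are collected, and the SAP may apply the right population. The reader might also want a non-return rate or a cumulative-incidence estimate to allow for disenrollment. The objectives ask for neither. Nor does the point bear on the end of exposed follow-up at receipt of any brand: Table 7 fixes that rule independently of this table.

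**Conclusion.** The contradiction stands as a stated population that gives a wrong result. Read literally, 8.7.1 fixes the type of the second and third dose at 100% study vaccine, leaves the other-brand category empty, and restricts timing to same-brand sequences. What is lost is the division of those without a same-brand next dose into another brand and no further dose, and the intervals for people who switched.

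This affects two of six secondary objectives, both descriptive. No relative risk, prevalence ratio, matching step, study-size figure or primary objective changes. The conclusion on type rests on reading the second and third dose as the ordinal COVID-19 dose; under the alternative reading the table is no longer strictly degenerate but still has the wrong population. The size of the practical loss is unknown, because the protocol gives no counts by brand, and the 85/3/12 split is only an illustration. The repeated clause in the third-dose sentence may come from text extraction and plays no part here.

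**What to change.** In Section 8.7.1, change the two conditioning phrases so that they match Section 7:

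- Second dose: among recipients of a first dose of the study vaccine, report the proportion whose second COVID-19 dose was the study vaccine and the proportion for whom it was another COVID-19 vaccine. Show no further recorded dose as the remainder, and give the time from first to second dose by type.
- Third dose: among recipients of 2 doses of the study vaccine, report the same for the third COVID-19 dose, with the time from second to third dose by type.

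Keep the subpopulations and age groups already listed, and carry the same populations into the SAP table shells. The cost is two sentences and a denominator change in descriptive tables. No extra data extraction is needed beyond what Section 8.3.1 already plans.

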8.7.2. Measures of disease frequency and association

All eligible individuals in each study cohort will be included in analysis of disease frequency and measures of association. However, in analysis of some safety events, individuals who have experienced the outcome in the recent past will be excluded from the analysis. This will be done to distinguish between FU care for events that have happened in the past from incident events occurring during FU. The washout periods for defining incident events will depend on the outcome and will be specified in the SAP.

8.7.2.1. Measures of disease frequency

In each data source, crude measures of incidence (for all outcomes except congenital malformations and small size for gestational age) or birth prevalence (for congenital malformations and small size for gestational age) with associated 95% CIs will be estimated within the matched exposed and unexposed cohorts. Prevalence will be estimated for major congenital malformations because the outcome is identified after birth without the ability to determine its true timing of onset during pregnancy. Prevalence will be estimated for small size for gestational age because the outcome is identified at a single timepoint (at birth).

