			•	Removed reproductive history including gravity, parity, spontaneous abortions, and pregnancy terminations from prior pregnancies as a covariate	women and remove reproductive history, which is incomplete in claims data
Version 4.0		Abstract, Section 8.7.2.2	•	Added measure of association and planned analyses for pregnancy outcomes (i.e., hazard ratios using Fine-Gray subdistribution proportional hazards models) and birth outcomes (i.e., Poisson regression to estimate prevalence ratios)	Clarify planned analyses for pregnancy and birth outcomes
Version 4.0		Abstract, Section 8.1, Section 8.7.3	•	Removed sensitivity analyses using historical comparator to assess potential misclassification for outcomes with gradual onset and/or risk intervals longer than 42 days and clarified historical comparator analysis will be used for pregnancy and birth outcomes	This analysis would be relevant for only one adverse event of special interest (AESI) (narcolepsy) and this AESI has not been listed as an AESI in the pharmacovigilance plan. This outcome will still be included in primary analyses.
Version 4.0		Section 8.2.3 and Section 8.2.4	•	Updated eligible population in Table 3 for stillbirth and preterm birth to include all eligible pregnancies Updated follow-up time to remove requirement to reach 20 weeks gestation	To avoid selection bias
Version 4.0		Section 8.2.3	•	Updated Tables 3-5 for clarity and consistency regarding inclusion and exclusion criteria Added criteria to Table 5 for Dose 3 analysis of pregnancy outcomes	Clarifications
Version 4.0		Section 8.3.1	•	Removed Table displaying codes for COVID-19 vaccines available in the United States as of 29 June 2022	Table was outdated, and available vaccines are evolving. Codelists for vaccines relevant at time of final analysis will be appended to the final statistical analysis plan

PFIZER CONFIDENTIAL CT24-WI-GL02-RF02 3.0 Non-Interventional Study Protocol Template For Secondary Data Collection Study 20-May-2021 Page 27 of 120

Amendment number	Date	Protocol section(s) changed		Summary of amendment(s)	Reason
Version 4.0		Section 8.3.2	•	Removed reference to "combinations of diagnosis codes for birthweight and gestational age" for definition of small size for gestational age	Updated to align with available information from data sources

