Table 3.	Eligible populations and exposure windows for analyses of pregnant
	women

Event	Eligible population	Exposure window
General safety events ^a	All eligible pregnancies	4 weeks before estimated pregnancy start to end of pregnancy
Pregnancy safety outco	omes	
Spontaneous abortion	All eligible pregnancies	4 weeks before estimated pregnancy start to end of pregnancy or 19-6/7 weeks of gestation, whichever is earlier
Stillbirth	All eligible pregnancies	4 weeks before estimated pregnancy start to end of pregnancy
Preterm birth	All eligible pregnancies	4 weeks before estimated pregnancy start to end of pregnancy or 36-6/7 weeks of gestation, whichever is earlier
Major congenital malformations	Singleton live deliveries with linkage to infant data available	4 weeks before estimated pregnancy start to 13-6/7 weeks of gestation (end of first trimester)
Small size for gestational age	Singleton live deliveries with linkage to infant data available	4 weeks before estimated pregnancy start to end of pregnancy

a. Safety events of interest listed in Table 8 in Section 8.3.2.1.

Analyses of major congenital malformations and small size for gestational age will require pregnancies to be linked to infants who have health plan enrollment from birth until age 3 months (or from birth until death if the infant dies before age 3 months). Where available, the Sentinel mother-infant linkage table (see Section 8.4) included in the most recently approved ETL (Extract, Transform, Load) at the time of the data extraction will be used for this study. Mother-infant linkage algorithms differ by data source and may use subscriber identification numbers and/or names and addresses; these algorithms will be described in the SAP.

8.2.3.1. Primary series analyses of general safety events, spontaneous abortion, stillbirth, and preterm birth in pregnant women

Cohort definitions for primary series analyses of general safety events, spontaneous abortion, stillbirth, and preterm birth are presented in Table 4. The primary series analysis will include dose 1, dose 2, and dose 3 if a third dose is received within 2 months of the second dose. Similar to the analytic approach in the general population, separate cohorts will be formed for each dose of Pfizer-BioNTech original monovalent COVID-19 Vaccine to assess these

PFIZER CONFIDENTIAL

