8.2.4. Follow-up

Events that can define the start and end of FU are provided in Table 7. Follow-up will end at the earliest of all possible events that define the end of FU.

Safety event of interest	Events defining the start of follow-up	Events defining the end of follow-up ^a
General safety events ^b		
	 Index date (if the risk interval starts on day 0), or One day after the index date (if the risk interval starts on day 1; see Table 8 in Section 8.3.2.1 for outcomespecific risk windows) 	 End of the study period End of data availability Disenrollment from the health plan Death Occurrence of the safety event of interest End of duration of the outcome-specific risk window (maximum of 1 year; see Table 8 in Section 8.3.2.1 for outcome-specific risk windows) Receipt of any brand of COVID-19 vaccine^c
Pregnancy safety outcomes		
Spontaneous abortion	 One day after the index date (if the index date is on or after estimated pregnancy start), or Estimated pregnancy start 	 End of pregnancy 20 weeks of gestation Receipt of and brand of COVID-19 vaccine^c

 Table 7.
 Events defining the start and end of follow-up

Safety event of interest	Events defining the start of follow-up	Events defining the end of follow-up ^a
Stillbirth	 One day after the index date (if the index date is on or after estimated pregnancy start) or Estimated pregnancy start 	 End of pregnancy Receipt of any brand of COVID-19 vaccine^c
Preterm birth	 One day after the index date (if the index date is on or after estimated pregnancy start) or Estimated pregnancy start 	 End of pregnancy 37 weeks of gestation Receipt of any brand of COVID-19 vaccine^c
Major congenital malformations ^d	• Day of birth	 End of study period End of data availability Disenrollment from the health plan Death Diagnosis of major congenital malformation Age 1 year
Small size for gestational age ^d	• Day of birth	• Predefined period shortly after birth (specific period to be defined in the SAP)

Table 7.	Events defining the start and end of follow-up
----------	--

COVID-19 = coronavirus disease 2019; FU = follow-up; SAP = statistical analysis plan.

a. For all analyses, the earliest of the listed events following the index date will mark the end of FU for each outcome. If FU ends due to the occurrence of a particular safety event of interest, FU will continue for all other safety events.

[figure not shown]
b. Safety events of interest are listed in Table 8 in Section 8.3.2.1.

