Respiratory	Acute respiratory distress syndrome	1-28
	Vaccine-associated enhanced respiratory disease	1-365
Other system	Anaphylaxis	0-1
	Appendicitis	1-42
	Kawasaki disease	1-42
	Multisystem inflammatory syndrome	1-42

COVID-19 = coronavirus disease 2019.

a. Time interval following vaccination when individuals will be followed for safety events of interest. Day 0 refers to the day of vaccination.

b. Sensitivity analysis will assess alternative risk interval definitions of 1-7 and 1-14 days.

The following pregnancy safety outcomes will be assessed in pregnant women or their infants:

- Spontaneous abortion: spontaneous pregnancy loss before 20 completed weeks gestation, identified using diagnosis codes
- Stillbirth: fetal deaths at or after 20 completed weeks gestation, identified using diagnosis codes

PFIZER CONFIDENTIAL

CT24-WI-GL02-RF02 3.0 Non-Interventional Study Protocol Template For Secondary Data Collection Study 20-May-2021 Page 69 of 120

- Preterm birth: live birth before 37 completed weeks gestation, identified using diagnosis codes
- Major congenital malformations: major congenital malformations will be identified in live-born infants using code lists from the National Birth Defects Prevention Network (NBDPN, 2021a), which defines a major defect as a congenital abnormality that requires medical or surgical treatment, has a serious adverse effect on health and development, or has significant cosmetic impact (NBDPN, 2021b)
- Small size for gestational age: less than 10th percentile of weight for gestational age, identified using diagnosis codes for small size for gestational age

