8.7.2.2. Measures of association

For comparative analyses of general safety events, Cox models or Poisson regression will be used to estimate RRs and 95% CIs within the matched cohorts. For pregnancy outcomes, hazard ratios and 95% CIs will be estimated using Fine-Gray subdistribution proportional hazards models (using gestational age as the time scale) to account for competing risks of other end-of-pregnancy events (e.g., termination, stillbirth) (Fine JP and Gray RJ, 1999).

For comparative analysis of small size for gestational age and major congenital malformations, modified Poisson regression (Zou, 2004) will be used to estimate prevalence ratios and 95% CIs within the matched cohorts.

For the dose 1 comparative risk estimation for general safety events and pregnancy outcomes, when a second dose of vaccine is administered before the risk interval following dose 1 is complete, the risk interval will be truncated at the time of dose 2, and FU after dose 2 will be excluded from the dose 1 risk estimation. In this situation, for the dose 2 comparative risk estimation, the risk interval will start on the date of the second vaccine dose and will extend for the duration of the risk interval for dose 2.

Similarly, for dose 2 comparative risk estimation for general safety events and pregnancy outcomes, when a third dose of vaccine is administered before the risk interval following dose 2 is complete, the risk interval will be truncated at the time of dose 3, and FU after dose 3 will be excluded from the dose 2 estimation. In this situation, for the dose 3 comparative risk estimation, the risk interval will start on the date of the third vaccine dose and will extend for the duration of the risk interval for dose 3.

For comparative analysis of outcomes identified separately in dose 1, dose 2, and dose 3 cohorts, comparative risks will be estimated separately by dose number. If comparative risk estimates are similar for dose 1, dose 2, and dose 3, then data from the dose 1 exposed/dose 1 unexposed cohorts, the dose 2 exposed/dose 2 unexposed cohorts, and the dose 3 exposed/dose 3 unexposed cohorts will be combined to obtain comparative risk estimates associated with at least 1 dose of the vaccine.

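### Crude stillbirth incidence counts follow-up before 20 weeks, when no stillbirth can occur, so the reported rates are too low and probably unequally so in the dose 1 cohorts

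*Protocol*

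**What the plan says.** - **Output.** Section 8.7.2.1 plans, with 95% confidence intervals in the matched exposed and unexposed cohorts, "crude measures of incidence (for all outcomes except congenital malformations and small size for gestational age"). Stillbirth is not among the exceptions. The text does not say whether incidence is a rate or a proportion.
- **Definition.** Section 8.3.2.1: "Stillbirth: fetal deaths at or after 20 completed weeks gestation, identified using diagnosis codes".
- **Exposure window.** Table 3 gives stillbirth the window "4 weeks before estimated pregnancy start to end of pregnancy", so index dates before 20 weeks are eligible.
- **Start of follow-up.** Table 7, stillbirth row: "One day after the index date (if the index date is on or after estimated pregnancy start"), otherwise estimated pregnancy start. There is no lower gestational limit.
- **End of follow-up.** Table 7: end of pregnancy or receipt of any COVID-19 vaccine. Note c to Table 7 ends dose 1 follow-up at dose 2. For comparative estimates, Section 8.7.2.2 says the same: "the risk interval will be truncated at the time of dose 2, and FU after dose 2 will be excluded from the dose 1 risk". Section 6 describes the two-dose schedule as three weeks apart.
- **Comparators.** Table 4 starts them at the gestational age of their exposed match. Table 7 follows them to the end of pregnancy unless they are vaccinated.
- **Measure of association.** Section 8.7.2.2 uses a Fine-Gray model with gestational age as the time scale.

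**The concern.** Time before 20 weeks can add to a stillbirth denominator but never to its numerator. A woman given dose 1 at week 6 and dose 2 at week 9 adds three weeks to the dose 1 stillbirth denominator and cannot add a case. Her unvaccinated comparator starts at week 6 as well but is followed to delivery, so much of that comparator's time is genuinely at risk.

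Two consequences follow. The absolute stillbirth rates, which a safety reader will take at face value, are understated. The exposed and comparator dose 1 rates may also be understated by different amounts, so that reading one against the other can suggest fewer stillbirths after dose 1 when there is no effect.

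Treating incidence as cases per woman does not remove the problem: a woman censored at week 9 then counts as a full non-case.

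**Working it through.** The protocol states no stillbirth rate or precision figure, so there is nothing of its own to reproduce.

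**Formula.** With a constant hazard h after 20 weeks and zero before, a cohort's crude rate is h × S, where S is the share of its person-time at or after 20 weeks. The rate is too low by the fraction 1 − S. With no vaccine effect, the crude rate ratio is S(exposed) / S(comparator).

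**One matched pair.** Dose 2 comes three weeks after dose 1 (Section 6). Assumed: delivery at 39 weeks and an unvaccinated comparator.

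- Index at week 10: exposed time is weeks 10 to 13, all before 20 weeks (100%). Comparator time is weeks 10 to 39, of which 10/29 = 34% is before 20 weeks.
- Index at week 18: exposed 2/3 = 67%, comparator 2/21 = 10%.
- Index at week 20 or later: 0% in both.

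**Whole cohorts, by simulation.** Assumptions not in the protocol: index dates uniform over the stated range; delivery normal with mean 39 and SD 1.8 weeks, limited to 21 to 42; the stated fraction of exposed women cut at index plus 3 weeks; comparators vaccinated at a constant weekly hazard.

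| Dose 2 uptake | Comparator vaccination per week | S exposed / S comparator, index -4 to 37 weeks | Ratio | S exposed / S comparator, index -4 to 20 weeks | Ratio |
|---|---|---|---|---|---|
| 90% | 0 | 0.577 / 0.693 | 0.83 | 0.376 / 0.619 | 0.61 |
| 90% | 2% | 0.577 / 0.657 | 0.88 | 0.376 / 0.557 | 0.68 |
| 60% | 0 | 0.659 / 0.693 | 0.95 | 0.555 / 0.619 | 0.90 |
| 60% | 2% | 0.659 / 0.657 | 1.00 | 0.555 / 0.557 | 1.00 |
| 60% | 3% | 0.659 / 0.640 | 1.03 | 0.555 / 0.527 | 1.05 |

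In the first row, the wide index range leaves the rates too low by 1 − 0.577 = 42% (exposed) and 1 − 0.693 = 31% (comparators). With index before 20 weeks the figures are 62% and 38%. In the rows with a ratio near 1, both rates are still too low; only the difference between them has gone.

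**If a proportion is reported.** With index uniform over 0 to 39 weeks, all exposed women receiving dose 2 at three weeks and no comparator vaccination, mean at-risk time after 20 weeks is about 1.5 weeks in the exposed and 14.4 weeks in comparators. The crude proportion ratio is then about 1.5/14.4 = 0.10 with no effect.

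**After the fix.** Counting from the later of the day after index and 20 weeks makes S = 1 in both cohorts. The crude rate ratio is 1.00 under no effect and a constant hazard.

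**The case against.** The strongest reply is that Section 8.7.2.1 does not spell out the denominator and Section 8.7 leaves detailed methodology to the SAP, which may define at-risk time properly. That limits the point: it holds if the stated follow-up, or all women indexed, is used as the denominator. It does not remove it, because Table 7 fixes the start of stillbirth follow-up explicitly and nothing in the protocol restricts that start for the crude figures.

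A second reply is that the planned comparison is the Fine-Gray hazard ratio on gestational age, where weeks before 20 hold no stillbirth events. That stands in full. No crude ratio is planned, and the crude cohorts are matched only on pregnancy start, state or region and maternal age, before propensity adjustment. The ratios above show what a reader would get by dividing two reported rates; they are not a planned estimate.

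A reader might infer that the crude rates will necessarily show a false deficit of stillbirth after dose 1. The documents do not support that. They give no gestational age at dose 1, no dose 2 uptake in pregnancy and no comparator vaccination rate, and the deficit disappears or reverses at 60% uptake with 2-3% weekly comparator vaccination. Note c to Table 4 also speaks of following both groups for the same duration, which would narrow the gap, although Table 7 has no rule that does this.

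Finally, the amendment log for Version 4.0 records "Updated follow-up time to remove requirement to reach 20 weeks gestation", with avoidance of selection bias as the reason. That is a sound reason to keep early-indexed pregnancies in the cohort. It is not a reason to count their early weeks as stillbirth person-time.

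**Conclusion.** The point holds for descriptive output only, and is minor. Under Table 7 as written, crude stillbirth incidence is too low in every cohort with members indexed before 20 weeks. That follows from the definition and the start of follow-up alone, whatever the vaccine effect. Greater dilution in the dose 1 exposed cohort is likely, because their follow-up stops at dose 2. Its size ranges from a crude ratio of 0.61 to no deficit at all across the scenarios tabulated, all of which assume a constant hazard after 20 weeks and inputs the protocol does not give. The hazard ratio for stillbirth does not carry this bias.

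Two inconsistencies bear on the same denominator. Table 3 makes all eligible pregnancies the stillbirth population, while Section 8.7.2.3.2.1 still gives pregnancies surviving past 20 completed weeks as the subset to be matched. Note c to Table 4 describes equal follow-up for exposed and unexposed women, while Table 7 ends follow-up at each woman's own next vaccination.

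**What to change.** 1. Keep all eligible pregnancies in the cohort at the index date. In Section 8.7.2.1 and Table 7, state that for crude stillbirth incidence person-time is counted only from the later of the day after index and 20 weeks 0 days.
2. State whether incidence is a rate or a proportion. If a proportion is reported, use a cumulative incidence by gestational age (Aalen-Johansen) that handles censoring at the next dose and treats other pregnancy ends as competing events.
3. Reconcile Section 8.7.2.3.2.1 with Table 3 on the stillbirth population, and note c to Table 4 with Table 7 on duration of follow-up.

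The cost is a few lines of text and one change to the person-time start in the program; the start-date change leaves cohorts, matching and the regression model as they are. The corrected crude rates will still not be an unbiased contrast if the stillbirth hazard varies after 20 weeks, because dose 1 exposed time lies closer to the index date. With a 10% per week change in hazard (an assumption), 90% uptake and no comparator vaccination, the corrected ratio under no effect is 0.94 to 1.06 for the wide index range and 0.95 to 1.08 for index before 20 weeks. The report should therefore point readers to the hazard ratio for comparison.
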